4.2.1.1 Management of diarrhoea

Diarrhoea is a known side effect of nintedanib treatment (see [Section 1.4.2](#)). However, potential causes for diarrhoea other than study medication should always be considered and treated accordingly (e.g. viral infections, bacterial overgrowth, antibiotic treatment).

Diarrhoea should be managed as early as possible after onset of first symptoms with standard antidiarrheal symptomatic treatment, e.g. loperamide.

If diarrhoea persists despite optimal symptomatic treatment, treatment interruption and/or dose reduction of nintedanib to 100 mg bid should be considered according to the recommendations described in [Table 4.2.1.1: 1](#).

Table 4.2.1.1: 1 Management of diarrhoea (considered related to trial medication)

Description	Symptomatic Treatment*	Action with trial medication
Diarrhoea with increase of <4 stools per day over baseline ¹ .	Initiate anti-diarrheal medicines at first signs of symptoms (e.g. 4 mg loperamide followed by 2 mg after each loose stool or every 2-4 hours to a maximum of 16 mg/day) until bowel movements cease for 12 hours.	Continue same trial medication dose.
Diarrhoea with increase of 4 to 6 stools per day over baseline ¹ .	Initiate/continue anti-diarrheal medicines; If diarrhoea of this severity persists for ≥48 to 72 hours assess for dehydration and electrolyte imbalance; In addition, consider IV fluids and electrolyte replacement as clinically indicated.	If diarrhoea persists for ≥48 to 72 hours despite optimal symptomatic care: 1. Interrupt trial medication until recovery. 2. Reduce dose to 100 mg bid after recovery. 3. Re-escalate to 150 mg bid within 4 weeks if deemed clinically appropriate.
Diarrhoea with increase of ≥7 stools per day over baseline ¹ ; stool incontinence, or life threatening consequences.	Follow recommendations above. In addition, consider stool work-up to exclude infectious colitis; adequate IV fluid replacement ≥24 hours, hospitalization as clinically indicated; consider referral to a GI specialist to rule out potential differential diagnoses.	1. Interrupt trial medication until recovery. 2. Reduce dose to 100 mg bid after recovery. 3. Consider re-escalation within 4 weeks to 150 mg bid if deemed clinically appropriate. In case of reoccurrence of diarrhoea of this severity despite optimal symptomatic treatment and dose reduction, treatment with trial medication should be permanently discontinued.

Footnotes:

* Other potential causes for diarrhoea should always be considered and treated accordingly (e.g. viral infections, SSc related diarrhoea, bacterial overgrowth, antibiotic treatment)

¹ Baseline defined as usual stools/day prior randomization.

4.2.1.2 Management of liver enzyme elevation

Nintedanib can be associated with increased liver enzymes (see [Section 1.4.2](#)). Concomitant use of other drugs known to cause liver enzyme elevations should be evaluated. For a detailed guidance on how to manage liver enzyme elevations, please refer to [Table 4.2.1.2: 1](#).

Table 4.2.1.2: 1 Recommendations for managing liver enzyme elevations

	AST and/or ALT increase to			Signs of hepatic injury* (Section 5.2.6)
	>1.5x to <3x ULN	≥3x to <5x ULN and no signs of hepatic injury (see Section 5.2.6)	≥5x to <8x ULN and no signs of hepatic injury (see Section 5.2.6)	
Visit 2 (randomization)	Withdraw trial medication or justify continuation ¹	Withdraw trial medication	Withdraw trial medication	Withdraw trial medication
Any other Visit	Continue as planned ²	Reduce dose or interrupt trial medication ³	Interrupt trial medication	Withdraw trial medication
		Close observation ⁴ After 2 weeks or any time later	Close observation ⁴ After 2 weeks or any time later	CLINICAL EVALUATION OF HEPATIC INJURY (Section 5.2.6.1.4)
	<3x ULN	≥3x ULN	< 3x ULN	≥3x ULN
	Reduced: return to initial dose. Interrupted: restart at reduced dose. Monitor bi- weekly for at least 8 weeks	Permanently discontinue trial medication Close observation ⁴	Restart at reduced dose Monitor weekly for 4 weeks, then bi-weekly for at least 8 weeks	Permanently discontinue trial medication. Close observation ⁴

Footnotes:

* Signs of hepatic injury are defined as

- ALT and/or AST ≥8 fold ULN
- ALT and/or AST ≥3 fold ULN and total bilirubin ≥2 fold ULN
- ALT and/or AST ≥3 fold ULN and unexplained INR >1.5
- ALT and/or AST ≥3 fold ULN and unexplained eosinophilia (>5%)
- ALT and/or AST ≥3 fold ULN and appearance of fatigue, nausea, vomiting, right upper abdominal quadrant pain or tenderness, fever and/or rash

¹ Investigator to confirm in writing that continuation is justified (e.g. intermittent fluctuation of transaminases).

² According to visit schedule. Consider additional control visits as adequate.

³ To be decided by Investigator, based on individual risk assessment.

⁴ Close observation: Re-test ALT and AST, alkaline phosphatase, total bilirubin, and eosinophils within 48 to 72 hours, then approximately 7 days, then approximately 2 weeks by using intermediate visit laboratory kit.

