3.3.5.1 Discontinuation of trial treatment

Short term interruptions for adverse events (see also [Section 4.2](#)) are possible and should be used whenever possible to avoid permanent discontinuation of trial medication

The following will require a permanent discontinuation of trial treatment of an individual patient:

- The patient wants to discontinue trial treatment, without the need to justify the decision.
- The patient can no longer receive trial treatment for medical reasons (such as chronic use of concomitant medication, adverse events, other diseases that puts a patient at risk, parenteral feeding requirement or pregnancy).
- The patient experiences signs of hepatic injury, defined in [Section 5.2.6.1.4](#).
- No further dose reduction is possible for patients on the 100 mg bid regimen. In case of persistent adverse events observed at this dose, or severe effects at 150 mg bid, permanent treatment discontinuation should be considered.

Temporary interruption (see also [Section 4.2.1](#)) or permanent discontinuation of trial treatment is recommended (at the investigators discretion) for the following situations:

- Major surgery, including any abdominal or intestinal surgery.
- Major thrombo-embolic events e.g. stroke, deep vein thrombosis, pulmonary embolism, myocardial infarction.
- Increased risk of bleeding e.g. hemorrhagic CNS event, haemoptysis or haematuria, active gastro-intestinal bleeding or GI-ulcers.
- The patient experiences an infection with SARS-CoV-2.

The investigator, after assessment of available clinical data and taking into consideration the potential risks associated with administration of nintedanib, may decide not to permanently discontinue the trial medication. In such a case, continuation of treatment with trial medication should be discussed with the patient, and the decision and reasoning documented in the source data.

If a patient becomes pregnant during the trial, the investigational product must be stopped and the patient should be followed up until birth or otherwise termination of the pregnancy. The data of the patient will be collected and reported in the clinical trial report (CTR) until patient's last visit and any events thereafter will be reported in the BI drug safety database. Refer to [Section 5.2.6.2.3](#) for detailed information on event reporting in case of pregnancy.

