4.2.2.2 Cautionary notes

Nintedanib is a substrate of P-gp and, to a minor extent, CYP3A4. Co-administration with oral doses of a potent P-gp and CYP3A4 inhibitors, e.g. ketoconazole, erythromycin, may increase exposure to nintedanib. In such cases, patients should be monitored closely. Management of adverse reactions may require interruption, dose reduction, or discontinuation of therapy with nintedanib.

Co-administration with oral doses of a potent P-gp and CYP3A4 inducers, e.g. rifampicin, carbamazepine, phenytoin, and St. John's wort may decrease exposure to nintedanib and should be avoided.

As the most common side effects known for nintedanib are GI effects i.e. diarrhoea, nausea and vomiting (see [Section 4.2.1.1](#)) the concomitant use of medication with an overlapping safety profile (e.g. mycophenolate mofetil) should be carefully considered.

Nintedanib is also associated with increases in liver enzymes and bilirubin. If in addition to the trial medication, a treatment is introduced that is known to induce AST/ALT elevations (e.g. methotrexate, bosentan), additional measurements of liver enzymes (ALT and AST, alkaline phosphatase, total bilirubin, and eosinophils) every 2 weeks for approximately 6 weeks, by using intermediate (a-visit) trial laboratory kit are recommended.

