5.2.3 Safety laboratory parameters

Safety laboratory parameters to be assessed are listed in [Table 5.2.3:1](#). For the sampling time points please see the [Flow Chart](#).

All analyses will be performed by a central laboratory, the respective reference ranges will be provided in the ISF.

Patients do not have to be fasted for the blood sampling for the safety laboratory.

Instructions regarding sample collection, sample handling/ processing and sample shipping are provided in the Laboratory Manual in the ISF.

The central laboratory will send reports to the investigator. It is the responsibility of the investigator to evaluate the laboratory reports. Clinically relevant abnormal findings as judged by the investigator will be reported as adverse events.

In case the criteria for hepatic injury are fulfilled, a number of additional measures will be performed (please see [Section 5.2.6.1.4](#) and the DILI Checklist provided in the ISF eDC system. The amount of blood taken from the patient concerned will be increased due to this additional sampling.

The central laboratory will transfer the results of the analysis to the sponsor.

Table 5.2.3:1 Safety laboratory tests

Category	Laboratory test
Haematology	Red blood cell count (RBC) Haemoglobin (Hb) Haematocrit (Hct) Mean corpuscular volume White blood cell count including differential Platelet count
Biochemistry	Aspartate aminotransferase (AST) Alanine transaminase (ALT) Gamma-glutamyl transferase (GGT) Alkaline phosphatase (ALK) Creatine kinase (CK) Lactate dehydrogenase (LDH) Total protein Total bilirubin Brain natriuretic peptide (BNP at V2, V7, V9 and EOT) Creatinine Glucose (non fasting) Uric acid

Table 5.2.3:1 Safety laboratory tests (cont.)

Biochemistry	Thyroid stimulating hormone (only at V2, V7, V9, and EOT)
Electrolytes	Sodium Potassium Calcium Chloride Inorganic phosphorus
Coagulation	International normalized ratio (INR) Activated partial thromboplastin time (aPTT) Prothrombin time (PT)
Urinalysis	pH, glucose, erythrocytes, leukocytes, protein, nitrite (semi-quantitative measurements; -, +, ++, +++)
	β-HCG will be performed at Visit 2 only, at central laboratory. Urine dipstick pregnancy tests will be provided by central laboratory and should be performed in all women of childbearing potential every 4-6 weeks. If urine test is not acceptable to local authorities, a blood test must be done at a local laboratory.

The laboratory tests at intermediate 'a' visits will include:

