Category	Laboratory test
Biochemistry	Total protein, creatinine, electrolytes and liver function (AST, ALT, GGT, alkaline phosphatase, and total bilirubin)
Urinalysis	pH, glucose, erythrocytes, leukocytes, protein, nitrite (semi-quantitative measurements; -, +, ++, +++)
Local Urine dipstick pregnancy test in all women of childbearing potential. If urine test is not acceptable to local authorities, a blood test must be done at a local laboratory.	

At 'a-Visits', safety blood, pregnancy tests and urine samples will be collected and submitted to the central laboratory if needed for additional safety monitoring at the discretion of the investigator (see [Section 4.2.2.2](#) for additional safety monitoring).

The samples and pregnancy tests may be collected at the office of a local doctor using trial specific lab kits that will be sent to a central laboratory for analyses. These kits will be provided to patients at study visits as applicable.

Creatinine clearance will be calculated based on serum creatinine according to Cockcroft and Gault ([R96-0690](#), [Appendix 10.2](#)).

If laboratory values indicate abnormality, adequate and more frequent blood sampling may be performed at the discretion of the Investigator.

In case of liver function value elevations, close monitoring must be ensured by the Investigator. Refer to [Section 4.2.1.2](#) for monitoring elevations and [Section 3.3.5](#) for withdrawal criteria.

Laboratory analysis will be done using central laboratory services. Venous whole blood will be collected through the assigned central laboratory. Details regarding centrifuge, processing, storage and shipment of samples will be determined by the central laboratory in accordance with the Sponsor. The Investigators will be informed and instructed by the central laboratory and detailed documentation will be included in the ISF.

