5.2.6.1.4 Adverse events of special interest

The term adverse events of special interest (AESI) relates to any specific AE that has been identified at the project level as being of particular concern for prospective safety monitoring and safety assessment within this trial, e.g. the potential for AEs based on knowledge from other compounds in the same class. AESIs need to be reported to the sponsor’s Pharmacovigilance Department within the same timeframe that applies to SAEs, please see [Section 5.2.6.2.2](#).

Adverse events relating to gastrointestinal perforation and hepatic injury will be considered AESIs.

Hepatic injury

In this trial protocol, signs of hepatic injury are defined as:

- ALT and/or AST \geq 8 fold ULN
- ALT and/or AST \geq 3 fold ULN and total bilirubin \geq 2 fold ULN*
- ALT and/or AST \geq 3 fold ULN and unexplained INR $>$ 1.5*
- ALT and/or AST \geq 3 fold ULN and unexplained eosinophilia ($>$ 5%)*
- ALT and/or AST \geq 3 fold ULN and appearance of fatigue, nausea, vomiting, right upper abdominal quadrant pain or tenderness, fever and/or rash

* in the same blood draw sample.

These laboratory findings constitute a hepatic injury alert and the patients showing these laboratory abnormalities need to be followed up according to the “DILI checklist” provided in the ISF.

In case of clinical symptoms of hepatic injury (icterus, unexplained encephalopathy, unexplained coagulopathy, right upper quadrant abdominal pain, etc.) without laboratory results (ALT, AST, total bilirubin) available, the investigator should make sure these parameters are analysed, if necessary in an unscheduled blood test. Should the results meet the criteria of hepatic injury alert, the procedures described in the DILI checklist should be followed.

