7.8.2 Laboratory data

The analyses of laboratory data will be descriptive in nature and based on SI units according to BI standards ([9.6](#)). Missing data will not be imputed.

Summary statistics of laboratory tests by functional group over time will be presented by treatment groups.

Potentially clinically significant abnormalities will be identified based on BI standard rules which are based on converted lab values, i.e., using SI units. Frequency tables will summarize the number of patients with potentially clinically significant abnormalities. In addition, lab shift tables will be presented.

Patients having an abnormal lab value at baseline will be presented in a listing separately. A separate listing will present all patients with potentially clinically significant lab values. In addition, a summary table will be prepared for the values outside of the clinically significant reference range including frequency and percentage of patients with abnormal values for relevant laboratory parameter.

A summary table of liver enzymes and bilirubin elevations over 52 weeks will also be provided. Liver enzyme and bilirubin elevations will be reported using the three following definitions:

- ALT and/or AST $\geq 8 \times \text{ULN}$
- ALT and/or AST $\geq 3 \times \text{ULN}$ AND total bilirubin $\geq 2 \times \text{ULN}^*$
- ALT and/or AST $\geq 3 \times \text{ULN}$ and unexplained INR $> 1.5^*$
- ALT and/or AST $\geq 3 \times \text{ULN}$ and unexplained eosinophilia ($> 5\%$) *
- ALT and/or AST $\geq 3 \times \text{ULN}$ and appearance of fatigue, nausea, vomiting, right upper abdominal quadrant pain or tenderness, fever and/or rash

* in the same blood draw sample.

A graphical analysis of the ALT and total bilirubin during the on-treatment period will also be performed according to BI standards ([9.6](#)), the so-called eDISH plot. For cases whose total bilirubin, AST/ALT values meet the criteria for Hy's Law (Maximum total bilirubin two or more times the ULN for the parameter, and the maximum ALT and/ or AST value three or more times its ULN) at any individual visit will be presented in a listing, showing the constituent values plus the associated alkaline phosphatase value at that time and the full course of available values for that case obtained during the study.

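### The kit named for liver re-tests has no white cell differential as printed, and INR is in neither re-test list, so two of five hepatic-injury signs go untested at those draws

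*Protocol*

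**What the plan says.** **Re-test lists.** Footnote 4 to Table 4.2.1.2:1 (Protocol 4.2.1.2) defines close observation: "Close observation: Re-test ALT and AST, alkaline phosphatase, total bilirubin, and eosinophils within 48 to 72 hours", repeated at about 7 days and about 2 weeks, with the intermediate visit kit. Protocol 4.2.2.2 covers patients who start another drug known to raise ALT/AST. It asks for ALT, AST, alkaline phosphatase, "total bilirubin, and eosinophils) every 2 weeks for approximately 6 weeks, by using intermediate (a-visit) trial laboratory kit are recommended".

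**What that kit covers.** Protocol 5.2.3 gives the blood tests at intermediate visits as "Total protein, creatinine, electrolytes and liver function (AST, ALT, GGT, alkaline phosphatase, and total bilirubin"). The rest of that panel is urinalysis and a local pregnancy test. Haematology ("White blood cell count including differential") and coagulation, including INR, appear only in the full panel, Table 5.2.3:1.

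**What counts as hepatic injury.** Protocol 5.2.6.1.4 lists five signs:
- ALT/AST at least 8× ULN;
- ALT/AST at least 3× ULN with bilirubin at least 2× ULN;
- ALT/AST at least 3× ULN with unexplained INR above 1.5;
- ALT/AST at least 3× ULN with unexplained eosinophilia above 5%;
- ALT/AST at least 3× ULN with listed symptoms.

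The bilirubin, INR and eosinophil signs must come from one blood draw. The section adds: "These laboratory findings constitute a hepatic injury alert".

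**What follows from a sign.** Protocol 3.3.5.1 includes this among the reasons for required permanent discontinuation: "The patient experiences signs of hepatic injury, defined in" section 5.2.6.1.4. In SAP 7.8.2, "A summary table of liver enzymes and bilirubin elevations over 52 weeks will also be provided", using the same five signs and the same one-draw rule.

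**The concern.** There are two separate faults. For eosinophils the protocol contradicts itself: two sections call for the test from a kit whose printed contents do not include it. For INR it is an omission: the test defines one of the five signs but is in neither re-test list nor the kit.

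The re-tests exist to show whether an enzyme rise has become hepatic injury, and the answer decides whether the patient may ever take the drug again. Suppose a patient has no sign at detection, then develops an isolated INR or eosinophil sign at 48 to 72 hours or about 7 days, with ALT/AST still at least 3× ULN. If the sign is not tested and ALT/AST then falls below 3× ULN, the table sends the patient back to the initial dose (if the dose was reduced) or restarts at the reduced dose (if interrupted). The protocol intends permanent withdrawal for that patient.

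The record is affected too. Because of the one-draw rule, a later full panel with ALT/AST below 3× ULN cannot recover the sign, so the SAP 7.8.2 table would miss it. Protocol 1.4.2 names Asian race as a risk factor for enzyme elevation and recommends close monitoring, and this trial enrols only Chinese patients.

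**Working it through.** No power or sample-size arithmetic applies. The check sets the printed lists side by side.

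**Step 1: analytes.**

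| Analyte | Footnote 4 | 4.2.2.2 | Intermediate panel (5.2.3) | Full panel (Table 5.2.3:1) |
|---|---|---|---|---|
| ALT | yes | yes | yes | yes |
| AST | yes | yes | yes | yes |
| Alkaline phosphatase | yes | yes | yes | yes |
| Total bilirubin | yes | yes | yes | yes |
| Eosinophils | yes | yes | **no** | yes (differential) |
| INR | **no** | **no** | **no** | yes |

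Footnote 4 names 5 analytes and the intermediate panel covers 4. The only leukocyte entry in that panel is in urine.

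**Step 2: signs that each list can support.** Symptoms are clinical and need only ALT/AST from the laboratory.

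| Sign | Intermediate panel | Footnote 4 list | Full panel |
|---|---|---|---|
| ALT/AST ≥8× ULN | yes | yes | yes |
| ≥3× with bilirubin ≥2× | yes | yes | yes |
| ≥3× with INR >1.5 | no | no | yes |
| ≥3× with eosinophilia >5% | no | yes | yes |
| ≥3× with symptoms | yes | yes | yes |
| **Total** | **3 of 5** | **4 of 5** | **5 of 5** |

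So mending the kit to match footnote 4 would still leave INR out.

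**Step 3: which re-tests can change drug action.** The first close-observation series has 3 draws: 48 to 72 hours, about 7 days, about 2 weeks. At about 2 weeks the table decides on ALT/AST alone. At 3× ULN or more the drug is stopped permanently anyway; below 3× ULN neither an INR nor an eosinophil sign can exist in that draw. That leaves 3 − 1 = 2 draws at which the missing tests could alter the decision.

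**Step 4: the added-drug recommendation.** Every 2 weeks for about 6 weeks gives 6 / 2 = about 3 draws per added drug.

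**Step 5: where the gap does not reach.**
- Scheduled visits use the full panel.
- Dose-change visits (6.2.4) probably do too. Their blood-draw sentence is the one used for Visits 3 to 6 and 8 in 6.2.2, while the intermediate-visit draw is worded differently.
- Visits 6a, 7a and 8a are ambiguous. The Flow Chart safety-laboratory row carries 14 marks for 14 visit columns, which appears to include them, so no claim is made about those visits.
- The panel is current body text, and the Global Amendment 3 entry gives the same list, so this is not a clash with superseded wording.

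**The case against.** The differences between the lists are not in dispute. The case on the other side is that little follows from them.

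- **The kit may hold more than is printed.** The panel is introduced as what the tests will include, and kit details sit in a laboratory manual outside these documents. A site following footnote 4 also has an explicit instruction to test eosinophils. This stands as a limit: the text shows a conflict, not a test that was missed. It does not help INR, which no re-test instruction names.
- **Investigators may test more.** Section 5.2.3 requires close monitoring of liver elevations and says "adequate and more frequent blood sampling may be performed at the discretion of the Investigator". That permission names neither test and does not settle a conflict between a specific instruction and its kit. The DILI checklist does not fill the gap either, because it starts only once the criteria are known to be met.
- **The clinical path is narrow.** A patient whose dose is reduced attends an extra visit, probably with the full panel, so one early draw is likely to be complete. A patient who is interrupted is off drug at the two re-tests that matter, and a restart is at the reduced dose with further monitoring. This stands and narrows the exposure. It does not cover the later re-tests, and restarting is still not what the protocol intends after a hepatic-injury sign.
- **An episode can have more than three re-tests.** Close observation is ordered again when ALT/AST stays at 3× ULN or more. That second series follows permanent discontinuation, so it has no drug decision left to change.
- **INR is an added test, and the SAP table is only descriptive.** Both are true. But INR defines one of the protocol's own signs, and a descriptive safety table still under-reports if a sign could not be observed.

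**Conclusion.** The concern holds in both parts. As printed, the intermediate kit does not cover the eosinophil test that footnote 4 and section 4.2.2.2 ask for, and INR is in neither list nor the kit. Two of the five signs that require permanent discontinuation would go untested at the close-observation and added-drug draws, unless the investigator orders extra tests or the physical kit holds more than the protocol lists.

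The number of patients affected and any extra time on drug cannot be estimated from the documents. The harm needs an isolated INR or eosinophil sign that is absent at detection, appears at an early re-test, and is followed by ALT/AST below 3× ULN. The primary endpoint, its analysis and the sample size are untouched. The mismatch in the printed text is certain; the clinical consequence depends on the unseen kit. It should be fixed because it concerns detection of liver injury and the remedy is cheap.

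**What to change.** Choose one of two routes for the kit:

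1. add a white cell differential and INR to the intermediate panel in Protocol 5.2.3; or
2. require the full Table 5.2.3:1 kit for any re-test prompted by ALT/AST at 3× ULN or more.

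In either case, add INR to the footnote 4 list and align section 4.2.2.2 with the panel chosen. With INR and the differential in place, the re-tests support 5 of 5 signs instead of 3.

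The cost is small: two more tests at draws already taken, both already in the central laboratory's full panel, plus wording in the protocol and laboratory manual. Global Amendment 4 records that an earlier revision to 5.2.3 was first clarified by administrative letter, so a quick route has been used before. The downsides are some added laboratory cost and the need to confirm sample stability, because section 5.2.3 allows these kits to be drawn at a local doctor's office and sent to the central laboratory.
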